VR has previously been tested in obesity¹⁻³, neurorehabilitation⁴⁻⁶, anxiety⁷⁻¹⁰ and pain management¹¹⁻¹⁸. For example, a meta-analysis of exposure therapies for anxiety disorders – e.g. PTSD, agoraphobia, panic disorder, social anxiety – reported large effects of VR on symptom reports at therapy termination.¹⁰ Similarly, a meta-analysis of post-stroke VR interventions found that patients experience reduced impairment and improved motor functioning with VR compared to usual care.⁶ In chronic pain, VR yields benefits for neck pain, procedure-related pain, and for cancer-related pain.¹¹ In burn care there is a greater reduction in pain and anxiety during bandage changes when patients use VR vs. pain medicines alone.¹² Also, burn patients report lower pain ratings and increased range of motion during physical therapy after immersion in a VR "snow world" that evokes a sense of cold to counteract the pain of a burn.¹³

In addition, the mediators of pain and stress are tied to activation of the hypothalamic-pituitary-adrenal (HPA) axis. Studies of experimental pain as well as acute and chronic pain demonstrate HPA activation through increases of circulating cortisol levels (McEwen BS, *Metabolism: Clin and Experimental*, 2010; Zimmer C, *Clin Journal of Pain*, 2003). Further, interventions to reduce pain can lead to decreases in cortisol levels. In one study of patients undergoing laparoscopic cholecystectomy randomized to exposure to music or no music, cortisol levels decreased in the music group (Graversen M, 2013). Similar findings were shown in a study of subjects undergoing colonoscopy (Uedo N, *Hepatogastroenterology* 2004). Another study demonstrated that chewing gum reduced salivary cortisol levels during a stress evoking procedure (Scholey A, *Physiol Behav* 2009).

With use of the virtual reality technology to reenact realistic experiences, the role of the HPA axis in pain pathways can be further studied. Administration of the Tier Social Stress Test (TSST) through virtual reality evokes a physiologic stress response in subjects and subsequent elevations in cortisol levels (Fallon MA, Psychosomatic Medicine 2016). Salivary cortisol levels may increase up to 30% on a TSST-VR intervention (Kelly O. 2007. Cyberpsychology & Behavior; Shibani Y. 2016. International Journal of Psychophysiology). However, not all studies confirm changes in cortisol (Montero-Lopez E. 2016. Behav Research; Kotlyar M. 2008. Psychophysiology). Mixed findings may be due to differential response of subjects classified as responders compared to nonresponders and the stressors used (Shibani 2016). Use of virtual reality to reduce endocrine biomarkers of acute pain has not been studied in a controlled setting.

However, despite all the evidence and recent media attention surrounding VR, there have been no controlled trials using VR at scale to manage inpatient pain. Our own work in VR has produced promising results consistent with previous VR research. We recently evaluated the feasibility of delivering VR to inpatients via a “Virtualist” consultation service, finding that VR was acceptable, particularly in younger patients.¹⁹ Further, we recently demonstrated that short-term exposure to a VR intervention called “Pain RelieVR”, developed by our partner organization (AppliedVR, Los Angeles, CA, USA), reduced reported pain scores by 24% pre- versus post-intervention across diverse surgical and medical inpatients.¹⁸ A sub-group analysis found that VR was effective for visceral pain from acute digestive disorders, including pancreatitis.²⁰

Taken together, this body of research suggests that VR interventions could be deployed as an adjunct to reduce opioid prescription for pain relief, and in some cases as an alternative to opioids. The suitability of the technology for use in a medical setting has been established by our own work, showing that VR is well-tolerated and enjoyed by patients.¹⁸ However, it remains untested if VR can improve patient and resource utilization outcomes at scale across diverse hospitalized patients in a controlled trial. Further, the effect of acute reductions in pain on endocrine biomarkers is unknown.

We will conduct a randomized controlled trial (RCT) of VR non-opioid management vs. a control “sham” intervention for a broad and representative group of medical and surgical patients with pain. Hospitalized patients will receive specialized VR interventions, administered via Samsung Gear headsets, to manage breakthrough pain. Control patients will view content on the in-room Health and Wellness television channel. We will follow patients throughout the course of their hospitalization and monitor outcomes during and after their stays. In addition, we will measure endocrine markers of stress as an optional procedure. Our multidisciplinary team of experts in VR, digital health science, mental health, and pain management will test an intervention that, if effective, could be used in resource-limited environments and serve as an adjunct for patients receiving opioids.

Specific Aims and Hypotheses:

The proposed RCT has the following aims:

1. Assess the relative benefits of using VR versus a control intervention for pain management – including pain scores, usage of pain medication, amount of time between pain medication requests, and complications from opioid pain medication – in a large cohort of hospitalized medical and surgical patients with pain.
2. Assess other characteristics of the hospital stay potentially affected by use of VR usage, including length of stay (LOS), and readmissions.
3. Assess patient satisfaction with general care and pain management following VR usage.

We hypothesize the following regarding these aims:

1. Relative to the control intervention, patients who use VR will report meaningfully reduced pain scores, will require less pain medication (opioid equivalents, and non-opioids), will report fewer opioid complications (e.g., nausea, vomiting, constipation), and will delay requests for breakthrough doses of pain medication.
2. Compared to controls, patients who use VR in the hospital will stay in the hospital for less time, report greater satisfaction with care, and will experience fewer readmissions.
3. Compared to controls, patients who use VR will report greater satisfaction with care, as measured by HCAHPS scores after 6 weeks of patient discharge

Exploratory aim:

1. Assess for reduction in cortisol levels with use of VR

Study Procedures:

Overview and Study Design

The study is an RCT that will enroll up to 244 inpatients with diverse diagnoses to test the efficacy of VR for long term pain management as an adjunct to opioid pain medication. We will randomize one group of patients to receive a VR-based intervention, and the other group of patients will receive a control “sham” intervention. We will randomize patients using the MS Excel random number generator to ensure that there is an equal distribution of participants in the control vs. experiment group. We will measure changes in self-reported pain, opioid pain medication usage (including breakthrough pain), time between doses, and other characteristics of the hospital visit. We will also assess patient satisfaction after 6 weeks using the HCAHPS survey. We will assess pre and post changes in pain between both the VR and control groups.

Originally, study participants were selected by an Investigator (Drs. [name], [name], [name], [name], [name], [name], [name], [name], [name], [name], [name], or [name]) and any other CSMC physicians who wished to refer their patients who met inclusion criteria. In the next phase of the study when the focus turns to orthopedic patients, CSMC physicians [name] and [name] and any other CSMC orthopedic physician will identify and refer orthopedic patients who meet inclusion criteria to participate in this trial. During the VR Intervention, we will place VR hardware on patients in their rooms, and allow

patients to use VR software for a 10-minute trial run. If they are interested, patients will be allowed to continue to use the VR software as needed for the remainder of their hospital stays. During the control “sham” intervention, patients will be instructed on the use of the in-room television system, and then shown 10 minutes of the Health and Wellness CARE Channel; these patients will be encouraged to repeat viewing as needed during the remainder of their hospital stays.

VR Intervention

[figure not shown]
As previously described, VR interventions have been used as distractions or diversions during medical procedures. This study will be one of the first RCTs to test deployment of low-cost VR as an adjunct to opioid pain management in an inpatient hospital setting. The VR hardware configuration and all software is currently being developed by AppliedVR, a leader in the development of medical applications for virtual reality technology, including interventions for weight loss and health, safety training, education, and personal development. Details about the VR hardware use can be found at the end of this document (See **VR Manual** in **Additional Information**), and are summarized below.

VR Hardware:

This RCT will utilize a Samsung Gear VR goggle set, fitted with a Samsung Galaxy phone that delivers VR images and sound (Figure 1a). Users will wear the VR goggles as shown in Figure 1b. Study staff will familiarize inpatients with hardware before use, and allow them to test use on their own before leaving the initial visit.

Figure 1. VR Hardware

1a. VR Goggles and Phone

1b. VR Goggles on user

VR Hardware Placement and Cleaning:

The Samsung gear device will be put in place as follows:

1. Patient places sanitary hairnet on head
2. Goggle is fitted with disposable foam backing affixed to inside of face mask
3. Study coordinator places goggle headset on patient and adjusts straps

Between patients, the device will be cleaned as follows:

1. Disposable hairnet on patient and foam backing will be thrown in sanitary waste bin in inpatient room.
2. Fabric strap will be cleaned by coordinator using Virex, approved cleaner for medical fabrics and let sit for a minimum of 10 minutes before next use.
3. Plastic housing of device will be cleaned using Sani-wipes and let sit for a minimum of 2 minutes before next use.
4. Inside and outside of the lenses of device will be cleaned using approved lens cleaner containing alcohol.

VR Software:

In VR, 3D visual and audio cues immerse the patient. Software modules may be used as needed during the inpatient stay for as long as a patient wishes. We are requiring 10 minutes for initial test use in the presence of study staff, and then recommending a maximum of 30 minutes at a time, each followed by 15 minute breaks. Patients will be shown how to select VR experiences from the phone menu (Figure 2).

Figure 2. VR Software Menu

VR interventions include the following (see Figure 3):

Figure 3. VR Environment Examples

- **Iceland Flyover:** Patients fly over photorealistic views of world landmarks, allowing them to visit famous places from the hospital bed.

3a. Iceland Flyover

- **Pain RelieVR:** Patients are immersed in a fantasy world where they use their gaze to direct objects at moving targets, while exposed to colorful imagery and soothing music.

3b. Pain RelieVR

- **Anxiety RelieVR:** Patients experience an interactive, meditative landscape along a peaceful shoreline.

3c. Anxiety RelieVR

Study Population and Period

The overall study population will consist of up to 244 patients – 122 patients who are exposed to VR, and 122 control patients exposed to an audiovisual “sham” intervention. We will randomize patients using the MS Excel random number generator. We will select up to 244 hospitalized patients at CSMC admitted during the study period of 1 October 2016 to 30 September 2018. The inpatient wards serve patients ranging in age from 18 to over 100, allowing us to assess the feasibility of using VR across diverse age groups. Initially, we did not restrict eligibility to any particular diagnosis, although we will collect this demographic information for subsequent subgroup analysis. All participants were selected at random by the Co-Investigator ([name]), by investigators in the gastroenterology service (Drs. [name] and [name]), or the Heart Institute (Drs. [name], [name], and [name]) or psychiatry service (Drs. [name] and [name]), or any CSMC physician who wishes to refer patients who meet the eligibility

criteria. However, preliminary analysis on patients enrolled in the study from 1 October 2016 to 30 September 2017 indicate that patients with higher baseline pain intensity experience greater reductions in pain as a result of VR when compared to the control group. Upon several subgroup analyses and communications with Cedars-Sinai providers, we determined a change in focus of diagnosis would improve the power of these analyses. The Cedars-Sinai Orthopedic Department has a large and steady supply of high severity pain patients that might benefit from a pain distraction intervention. The department's physicians have also expressed a strong interest in alternative pain treatment modalities and would like to explore these distraction methods further. We will use the existing protocol to continue to recruit only hospitalized orthopedic patients for a full cohort of 160 orthopedic patients for this trial. Because our currently enrolled sample (1 October 2016 to 30 September 2017) already includes some orthopedic patients, we will recruit only additional orthopedic patients until we complete the cohort of 160 orthopedic patients, accounting for possible withdrawal from the study. Once this cohort of patients is complete, the overall sample size for the entire study including patients from all diagnosis groups will be up to 244 patients.

Eligibility Criteria

The following criteria will be used to define patient eligibility:

Inclusion Criteria:

- Able to understand the goals of the study and provide informed consent
- Until 30 September 2017, any hospitalized patient under care of CSMC inpatient service (ISP), gastroenterology, or psychiatry, admitted between 1 October 2016 and 30 September 2017, who is not excluded due to criteria listed below.
- From 1 October 2017 Until 30 September 2018, any hospitalized patient under the care of CSMC orthopedic providers
- At least 18 years of age
- English speaking

Exclusion Criteria:

- Unable to consent to study due to cognitive difficulty
- Current diagnosis of epilepsy, dementia, or other neurological disease that may prevent use of VR hardware and software
- Sensitivity to flashing light or motion
- Pregnancy, or a medical condition where the patient is prone to frequent nausea or dizziness
- Recent stroke
- Post-transplant patient, or pre-transplant patient with severe illness
- Patient on ventilator, BiPAP, or other breathing assistance equipment

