response rate of approximately 25%. We will use these data to estimate changes in satisfaction associated with exposure to the intervention condition, versus the control condition. The HCAHPS survey has demonstrated face validity in previous studies.²⁸

Salivary cortisol assay (OPTIONAL):

The salivary cortisol assay will be processed at the lab at CSMC which is then shipped to Quest Diagnostics. It is stable at room temperature for 5 days. The assay is performed using liquid chromatography/tandem mass spectrometry. While cortisol has a diurnal variability with levels highest in the early morning, we will be assessing percent change of cortisol levels over the 10 minutes of the VR demonstration or Health and Wellness channel viewing in each individual. This will minimize the effect of the diurnal variation.

Data Collection

We will collect the following information about VR intervention and Control participants:

- Name and Medical Record Number (secured and stored separate from all other data below)
- Age
- Sex
- Race/Ethnicity
- Admitting Diagnosis during inpatient stay
- ISP ward
- Previous diagnoses of epilepsy and other neurological or visual impairments.
- All Pain ratings throughout the hospital stay.
- All opioid and non-opioid pain medication usage information (dosage amount and timing).
- HCAHPS Patient Satisfaction Picker Survey responses.

Demographic and descriptive clinical data will be abstracted by [name] or authorized study staff at the time of patient selection, and vital signs will be collected before and after the intervention.

Analysis Plan:

The current study plan allows us to enroll an average of three patients per week at a minimum.

We will calculate descriptive statistics for patients in each group. We will then perform bivariate analyses to compare mean cumulative pain scores, morphine milligram equivalents, and average length of stay between groups using t-tests. We will compare the proportion with an opioid complication between groups using chi-squared, and calculate the “number needed to treat” in order to prevent one additional complication with VR vs. no usual care. We will then perform multivariable linear regression analysis to predict pain scores while controlling covariates, including age, demographics, comorbidities, and baseline pain scores. We will report both intention-to-treat analyses including all evaluable patients

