by randomized allocation, and per-protocol analyses limited to just those patients in the intervention arm who opt to use VR (while accounting for dose-response potential). We will adopt a P-value of <0.05 as evidence for statistical significance, and calculate 95% confidence intervals around point estimates. All analyses will be performed using Stata for Windows (StataCorp, College Station, TX).

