We have powered this study based on our previous research on pain management with VR¹⁸⁻²⁰, which reported clinically meaningful shifts of approximately 1 SD in self-reported pain scores following brief exposure to VR. Several previous studies²¹⁻²³ have established that the minimal clinically important difference on patient-reported pain rating scales (visual analog or numerical ratings) is approximately 13% (approximately 1.4 points on a 0-10 scale, with a standard deviation of 14%). Thus, we are interested in measuring a 1SD change in pain ratings following exposure to the VR intervention, but we will collect a sufficiently large sample to measure smaller changes both within patients exposed to VR, and in comparison to a control group. For all analyses, we will assume a 5% Type I error rate (alpha) and a 20% type II error rate (or 80% power). For **within group analyses**, we would require a minimum of 10 patients to detect a 1 SD change in pain scores. However, we have powered the study to detect a 0.38 SD difference **within each group** (with 58 patients per group), however have modified this to 80 patients per group. We used this method to calculate and justify the required sample size for a complete cohort of orthopedic patients. Therefore, the overall intervention and control groups, along with the orthopedic subgroup will be adequately powered for analysis. The sample-size modification is required due to over-estimation of adherence, and aims to support a "per-protocol" analyses. We plan on conducting this per protocol analysis among treatment-compliant subjects *in addition* to the intent to treat analysis. The additional subjects, then, will bring the total N of the per-protocol analysis into a range capable of detecting the hypothesized effect-size used in the original sample-size calculation. While sample-size re-estimation based on observed difference with a limited number of subjects may be biased and misleading, we feel that the goal of the trial (determining efficacy rather than effectiveness) - coupled with the fact that randomization procedures will remain unchanged - supports the request.

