For **between group analyses**, we will compare pain scores obtained from all inpatients exposed to the VR intervention to a **80-patient control group**. We expect the variability in pain scores to be comparable to that observed in VR intervention participants (approximately 1 SD change over a 20-minute period, equivalent to an effect size of 1.0), so we are collecting data from the same number of patients (80) with complete data in Phase 2. We have powered this study to detect an SD difference as low as 0.52 between the VR intervention and control participants (requiring 80 patients in each group).

We will conduct an exploratory **subgroup analysis** to detect changes in salivary cortisol between patients exposed to VR vs patients exposed to the control intervention.

As of September 2017, 9 patients have been consented to participate in this sub-study, but only 1 patient yielded sufficient quantity of samples for a pre- and post-intervention cortisol analysis. The majority of samples were of inadequate quantity for laboratory analysis. Given that all participants eligible to participate in the main study are also eligible for this sub-study, each patient consenting to the main study will be asked to participate in the cortisol sub-study. Accounting for attrition and the

technical complexities of cortisol sampling that often results in low yield quantities, we will recruit 113 patients total (including the 9 that have already been consented as of September 2017).

Risks and Benefits:

Benefits:

To Individual: Patients will likely enjoy using the VR interventions, which are immersive and impressive upon cursory use. We anticipate that patients may report greater satisfaction, pain management, and overall health during the study.

To Society: This will be one of the first RCTs conducted on inpatient use of VR for pain management. Knowledge gained could be used to improve patient satisfaction with care and pain management across all hospitals.

Risks:

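### All-patient comparisons name neither orthopedic status nor enrolment phase as covariates: a loss of precision only, of unknown size, and free to remove

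*Combined protocol and SAP*

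**What the plan says.** Study Population and Period describes two recruitment regimes. Until 30 September 2017 patients came from several services without restriction by diagnosis; from 1 October 2017 only orthopedic inpatients are recruited. The stated reasons for the change are that patients with higher baseline pain gained more from VR, and that orthopedics supplies patients with severe pain. At the end, "the overall sample size for the entire study including patients from all diagnosis groups will be up to 244 patients". Patient Recruitment and Study Procedures puts 160 of these in orthopedics. The first-phase sample already holds some orthopedic patients; their number is not given.

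Randomisation uses the Excel random number generator, with no strata described. The Control Group section adds that the team will try to match controls on age, sex, ethnicity and admitting diagnosis, gives no method, and keeps the analysis as a between-subjects comparison.

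The Analysis Plan compares cumulative pain scores, morphine equivalents and "average length of stay between groups using t-tests", and opioid complications by chi-squared. One linear regression follows, for pain scores only, "controlling covariates, including age, demographics, comorbidities, and baseline pain scores". The power text, also in the Analysis Plan, treats both the overall groups and the orthopedic subgroup as adequately powered, so the all-patient comparison is an intended analysis.

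**The concern.** The plan changed its population because it expected orthopedic patients to differ in pain, and possibly in benefit. An all-patient t-test puts any outcome difference between the two populations into the error term, which widens the confidence interval. For morphine equivalents, length of stay and complications no adjusted analysis is planned at all. For pain there is one, but the two variables that define the pooled populations are not named in it. Both are fixed before randomisation and already held for every patient, so precision is given up for no return. A single pooled estimate also does not show whether an overall effect is present in the 84 non-orthopedic patients, for whom no between-arm estimate of their own is specified.

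**Working it through.** **Inputs from the documents.** 122 per arm; 160 orthopedic of 244, so p = 160/244 = 0.656 and 1 − p = 84/244 = 0.344; 5% alpha and 80% power; "We will adopt a P-value of <0.05 as evidence for statistical significance", read here as two-sided because sidedness is not stated.

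**Input not in the documents.** The gap g between orthopedic and other patients on an outcome, in units of the within-population SD. Assumed range: 0.25 to 1.0.

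**The plan's own figure.** The power text states: "We have powered this study to detect an SD difference as low as 0.52 between the VR intervention and control participants". It gives the size needed for this as 80 per arm. The detectable difference is (1.960 + 0.842) × √(2/n):
- n = 58: 2.802 × √(2/58) = 0.520 SD
- n = 80: 2.802 × √(2/80) = 0.443 SD

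So 0.52 SD belongs to the earlier target ("with 58 patients per group"), not to 80. That is a separate matter and does not affect this point.

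**Detectable difference with the population term.** At 122 per arm: 2.802 × √(2/122) = 0.359 SD. This ignores the degree of freedom used.

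**Without the term.** The outcome variance is v = 1 + p(1 − p)g², with p(1 − p) = 0.656 × 0.344 = 0.2257. The detectable difference is 0.359 × √v, the effective sample size is 244/v, and the share lost is 1 − 1/v.

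| Assumed gap g | v | Detectable difference (SD) | Effective N | Loss | Power at a true 0.36 SD |
|---|---|---|---|---|---|
| Adjusted | 1 | 0.359 | 244 | – | 80.3% |
| 0.25 | 1.014 | 0.361 | 241 | 1.4% | 79.7% |
| 0.5 | 1.056 | 0.369 | 231 | 5.3% | 78.1% |
| 0.75 | 1.127 | 0.381 | 217 | 11.3% | 75.4% |
| 1.0 | 1.226 | 0.397 | 199 | 18.4% | 71.9% |

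At the plan's 0.52 SD, power with 244 patients is 98.2% with the term and still 95.6% without it at g = 1.

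**Chance imbalance.** Under simple randomisation the orthopedic share differs between arms with SD √(2p(1 − p)/122) = 0.061. At g = 1 this moves the estimate with SD 0.061, a variance of 0.0037. The variance added in the table is 2 × (1.2257 − 1)/122 = 0.0037. These are the same quantity, so imbalance is not a second cost.

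**Type I error.** In 20,000 simulated trials per gap, with no arm effect, the unadjusted t-test rejected in 5.0% (g = 0.5) and 4.9% (g = 1); with the term, 5.0% and 4.9%.

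**Scope.** The table applies to continuous outcomes and compares with the unadjusted t-test. It does not include a phase term. From 1 October 2017 all recruits are orthopedic, so only three of the four phase-by-diagnosis cells are occupied, and a phase effect is estimated from orthopedic patients alone.

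**The case against.** **Adjustment for pain may largely exist.** The planned regression includes baseline pain, the feature that motivated the switch. The covariate list is open, and Study Population and Period calls diagnosis demographic information, so demographics might be meant to cover it. This stands in part: the gain over that regression cannot be computed from the documents. But the same sentence assigns diagnosis to subgroup analysis, Data Collection lists admitting diagnosis as its own item, and the regression does not extend to the other outcomes.

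**Balance is already sought.** The Control Group section plans matching on admitting diagnosis, and targets of 80 orthopedic and 122 total per arm imply 80/80 and 42/42. Effective matching would reduce the imbalance computed above. It would not shorten the interval from an unadjusted t-test, whose error term would still contain the population difference; the factor has to be in the model.

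**Stronger readings.** A reader might infer that chance imbalance biases the overall result or inflates false positives. With allocation randomised as described, it does neither. A reader might also take the 18% loss, about 45 patients (244 − 199), as the expected size. It needs a 1 SD gap, which nothing in the documents supports: they call orthopedic pain severe but give no comparison figure, and say nothing of how opioid use or stay differ.

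**Subgroup work is already planned.** The orthopedic cohort has its own analysis and diagnosis is kept for subgroups. That does not improve the all-patient tests.

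**Conclusion.** The point holds as a free improvement. The all-patient analyses pool two populations and two phases without naming either in any model, and three of the four outcome comparisons have no adjusted analysis. The consequence is lost precision: about 1% to 5% of effective sample size at gaps of 0.25 to 0.5 SD, and 18% only if the gap reaches 1 SD. The plan's stated target of 0.52 SD is not threatened in any of these cases. The figures rest on an assumed gap, a common within-population SD, 122 per arm, a two-sided 5% test and random allocation without effective matching. For pain scores the true gain over the planned regression may be smaller and is unknown.

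**What to change.** In the Analysis Plan:

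- Make the all-patient between-arm analysis of each continuous outcome a model with arm, orthopedic status (yes/no) and enrolment phase (before, or from, 1 October 2017). Keep the last two as separate covariates, because the first phase includes orthopedic patients.
- Add baseline pain for pain scores. Length of stay has no baseline value and needs none.
- Compare opioid complications with a Mantel-Haenszel analysis stratified by the same factors, on the risk-difference scale so that the planned number needed to treat follows from it.
- Report the arm effect with its confidence interval separately in orthopedic and non-orthopedic patients. With about 42 per arm the latter can detect only 2.802 × √(2/42) = 0.61 SD, so present it as descriptive.
- State how matching on admitting diagnosis works alongside randomisation. If it is done, keep that factor in the model.

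The cost is wording only. Diagnosis and admission date are known for every patient, and no extra patients or data are needed. The terms should be fixed before any further unblinded look at outcomes.
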